## Appendix 6. Classification of Contraceptive Methods

---

**Highly Effective Methods of Contraception:**

- Combined oral contraceptive pill and mini pill
- NuvaRing
- Implantable contraceptives
- Injectable contraceptives (such as Depo-Provera®)
- Intrauterine device (such as Mirena® and ParaGard®)
- Contraceptive patch – ONLY women <198 pounds or 90 kg
- Total abstinence or in a same-sex relationship (if this is their preferred and usual lifestyle). Note: periodic abstinence (for example, calendar, ovulation, symptothermal, postovulation methods), declaration of abstinence just for the duration of a trial, and withdrawal are not acceptable methods of contraception
- Vasectomy – for men in clinical trials

**Effective Methods of Contraception (must use combination of 2 methods):**

- Male condom with spermicide
- Female condom with spermicide
- Diaphragm with spermicide
- Cervical sponge
- Cervical cap with spermicide

---

## Appendix 7. Pancreatic Monitoring

---

Glucagon-like peptide-1 agonists have been associated with a possible risk of acute pancreatitis. Epidemiologic studies have indicated that there is an increased incidence and prevalence of pancreatitis in persons with T2DM.

To enhance understanding of the natural variability of pancreatic enzymes in the T2DM population and, in order to assess for any potential effects of tirzepatide on the exocrine pancreas, amylase and lipase values will be monitored in all current and future clinical trials with tirzepatide.

Additional monitoring will be requested for amylase or lipase values  $\geq 3 \times$  the ULN at any visit, even in asymptomatic subjects (see figure below). Lipase and amylase may also be obtained at any time during the clinical trials for any subject suspected of having symptoms suggestive of pancreatitis (such as severe GI signs and/or symptoms), at the investigator's discretion.

[figure not shown]
Acute pancreatitis is an AE defined as an acute inflammatory process of the pancreas that may also involve peripancreatic tissues and/or remote organ systems. The diagnosis of acute pancreatitis requires 2 of the following 3 features:

- abdominal pain characteristic of acute pancreatitis
- serum amylase and/or lipase  $\geq 3 \times$  ULN
- characteristic findings of acute pancreatitis on computed tomography scan or magnetic resonance imaging

Most subjects with acute pancreatitis experience abdominal pain that is located generally in the epigastrium, and radiates to the back in approximately one-half of the cases. The pain is often associated with nausea and vomiting. However, experience with GLP-1 agonists has demonstrated that some subjects asymptomatic for classic pancreatitis may demonstrate significant elevations of lipase and/or amylase. For subjects considered by investigators to be asymptomatic for pancreatitis, but whose value(s) for lipase and/or amylase are  $\geq 3 \times$  ULN, an algorithm is in place to follow these subjects safely and to quickly reach (or not reach) a diagnosis of pancreatitis.

## Pancreatic Enzymes: Safety Monitoring Algorithm for Subjects/Patients without Symptoms of Pancreatitis

Follow this algorithm when the value(s) for serum lipase and/or amylase are  $\geq 3$  X ULN.

1. Symptomatic – related primarily to abdominal pain consistent with pancreatitis; however, severe nausea, vomiting and other symptoms may be considered by the investigator as symptomatic as well.

2. If, at any time, in the opinion of the investigator, patient/subject has symptoms of acute pancreatitis irrespective of L/A results:

- (a) Consult appropriate specialist for assessment and management
- (b) Assess for causes of pancreatitis
- (c) Stop study drug (if applicable)
- (d) Notify Lilly

3. L/A = Lipase and/or amylase. Either or both enzymes can be measured and either or both can be used to meet the algorithm criteria.

4. Abdominal imaging is most valuable when performed at the time of elevated enzyme values. If in the opinion of the radiologist or investigator, it is safe for the patient/subject to receive contrast, an enhanced abdominal CT is preferred. MRI is also an acceptable imaging modality.

5. As minimum, test hepatic analytes, triglycerides, and calcium, and record all concomitant medications

6. Imaging results positive or negative for signs of acute pancreatitis

Abbreviations: CBC = complete blood count; CT = computed tomography; LFTs = liver function tests; MRI = magnetic resonance imaging.

Subjects diagnosed with pancreatitis will be discontinued from the study. Investigators will be responsible for following, through an appropriate healthcare option, these pancreatitis AEs until the events resolve or are explained. Adverse events that meet the diagnostic criteria of acute pancreatitis will be captured as SAEs. For all other pancreatic AEs (such as idiopathic or asymptomatic pancreatic enzyme abnormalities), the investigator will be responsible for determining the seriousness of the event (AE or SAE) and the relatedness of the event to study drug.

---

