Blood Glucose Monitoring (hours)			Predose, 8, 12	24, 36	48	72	96	X	X	X		Performed using a bedside glucose monitor. Additional measurements may be taken at the discretion of the investigator as clinically indicated.
PK Sampling (hours)			Predose, 8, 12	24	48	72	96	168	336	X		The exact time of sampling must be recorded.

Abbreviations: AE = adverse event; CRU = clinical research unit; D = day; ECG = electrocardiogram; ED = early discontinuation; PK = pharmacokinetic(s);

TE ADA = treatment-emergent antidrug antibodies.

Note: All sampling times are given relative to dosing (Time 0 hour) with tirzepatide (predose or hours postdose).

If multiple procedures take place at the same time point, the following order of the procedures should be used: ECGs, vital signs, clinical laboratory sample, PK sample (record of actual PK sampling time is the priority), immunogenicity, blood glucose and pharmacogenetic sample.

a Specified times are approximate and actual times will be recorded. Actual time should not exceed 1 hour prior to dosing for the predose assessment.

b Screening sample and any unscheduled samples for immediate safety assessments may be performed by the local laboratory affiliated with the sites. All other scheduled clinical safety laboratory samples will be assayed by a central laboratory for study reporting purpose.

c At least 28 days postdose or within 7 to 14 days upon confirmation of early discontinuation.

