## 5. Study Design

### 5.1. Overall Design

This will be a multicenter, parallel, single-dose, open-label, single-period study of tirzepatide in subjects with normal hepatic function and subjects with mild, moderate, and severe hepatic impairment. Subjects who have a concomitant T2DM diagnosis will not be specifically excluded.

Subjects will be enrolled within the following groups:

- Group 1: at least 6 subjects and up to 12 subjects with normal hepatic function (Control).
- Group 2: at least 6 subjects with mild hepatic impairment (Child Pugh [CP] A).
- Group 3: at least 6 subjects with moderate hepatic impairment (CP B).
- Group 4: up to 6 subjects with severe hepatic impairment (CP C).

Efforts will be made to achieve 6 completers with severe hepatic impairment (Group 4); however, acknowledging the difficulty in recruiting this subject population, 2 to 3 subjects with severe hepatic impairment may be an acceptable target.

The Child-Pugh classification is described in Section [5.1.1](#).

[figure not shown]
Subjects enrolled in Group 1 (normal hepatic function) will be matched by weight ( $\pm 10$  kg), age ( $\pm 10$  years), and sex to subjects in Groups 2 through 4, as far as practically possible. Subjects with normal hepatic function cannot be matched to more than 1 hepatically-impaired subject within an impairment group; however, subjects with normal hepatic function may be matched to 1 subject from more than 1 hepatic impairment group, therefore requiring fewer subjects to be enrolled to Group 1 (minimum of 6). Subjects who withdraw before completing all study procedures may be replaced at the discretion of the investigator in discussion with the sponsor.

Subjects will undergo a screening examination within 28 days prior to enrollment, check in to the CRU on Day -1, and receive a single SC dose of 5 mg tirzepatide on Day 1, following an overnight fast of at least 8 hours. Subjects will remain at the CRU until discharge on Day 5, and return to the CRU on Days 8 and 15 for PK blood sampling and other study procedures. Each subject will be required to return to the CRU for a follow-up visit and final PK blood sample collection at least 28 days postdose.

Pharmacokinetic blood sampling and safety assessments, including vital sign measurement, physical examination, clinical laboratory tests, electrocardiograms (ECGs), and AE recording, will be performed according to the Schedule of Activities (Section [2](#)).

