- [30] show evidence of significant active neuropsychiatric disease
- [31] have a history of malignancy within 5 years prior to screening
- [32] have a history or presence of pancreatitis (history of chronic pancreatitis or idiopathic acute pancreatitis), elevation in serum amylase and/or lipase  $>1.5 \times$  the upper limit of normal (ULN) or GI disorder (eg, relevant esophageal reflux or gall bladder disease) or any GI disease which impacts gastric emptying (eg, gastric bypass surgery, pyloric stenosis, with the exception of appendectomy) or could be aggravated by GLP-1 analogs or dipeptidyl peptidase-IV inhibitors. Subjects with dyslipidemia and subjects who had cholecystolithiasis treatment (removal of gall stones) and/or cholecystectomy (removal of gall bladder) in the past, with no further sequelae, may be included in the study at the discretion of the investigator.
- [33] have serum AST or ALT  $>2 \times$  ULN or total bilirubin  $>1.5 \times$  ULN (applies to Group 1 control subjects only)
- [34] have a serum triglyceride  $\geq 5$  mmol/L (442.5 mg/dL) at screening (applies to Group 1 control subjects only)
- [35] show evidence of human immunodeficiency virus (HIV) infection and/or positive HIV antibodies
- [36] show evidence of hepatitis C and/or positive hepatitis C antibody (applies to Group 1 control subjects only)
- [37] show evidence of hepatitis B and/or positive hepatitis B surface antigen (applies to Group 1 control subjects only)
- [38] are women with a positive pregnancy test or women who are lactating
- [39] regularly use known drugs of abuse and/or show positive findings on urinary drug screen that are not otherwise explained by permitted concomitant medications
- [40] intend to use:
  - a. over-the-counter medication within 7 days prior to dosing (except for hepatic impairment and T2DM subjects on stable doses)
  - b. prescription medication (other than those listed in Section 7.7 and [Appendix 9](#)) within 14 days prior to dosing
  - c. herbal preparations within the 14 days prior to screening

If any of the above situation arises, an otherwise suitable subject may be included at the discretion of the investigator.

- [41] have donated more than 450 mL blood, including plasma and platelets, within 1 month prior to Check-in

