**Table GPGQ.3. Treatments Administered**

Treatment Name	Tirzepatide
Dosage Formulation	Prefilled syringe
Dosage strength	2.5 mg / 0.5 mL or 5 mg / 0.5 mL
Route of Administration	Subcutaneous
Dosing instructions	Single injection into abdomen on Day 1

The investigator or designee is responsible for:

- explaining the correct use of the investigational product to the site personnel
- verifying that instructions are followed properly
- maintaining accurate records of investigational product dispensing and collection
- and returning all unused medication to Lilly or its designee at the end of the study

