### **9.2.1. Serious Adverse Events**

An SAE is any AE from this study that results in one of the following:

- death
- initial or prolonged inpatient hospitalization
- a life-threatening experience (that is, immediate risk of dying)
- persistent or significant disability/incapacity
- congenital anomaly/birth defect
- important medical events that may not be immediately life-threatening or result in death or hospitalization but may jeopardize the subject or may require intervention to prevent one of the other outcomes listed in the definition above.

Study site personnel must alert the Lilly CRP/CP, or its designee, of any SAE as soon as practically possible.

Additionally, study site personnel must alert Lilly Global Patient Safety, or its designee, of any SAE within 24 hours of investigator awareness of the event via a sponsor-approved method. If alerts are issued via telephone, they are to be immediately followed with official notification on study-specific SAE forms. This 24-hour notification requirement refers to the initial SAE information and all follow-up SAE information.

Although all AEs are recorded in the eCRF after signing informed consent, SAE reporting to the sponsor begins after the subject has signed informed consent and has received investigational product. However, if an SAE occurs after signing informed consent, but prior to receiving investigational product, AND is considered reasonably possibly related to a study procedure then it **MUST** be reported.

Investigators are not obligated to actively seek AEs or SAEs in subjects once they have discontinued from and/or completed the study (the subject summary eCRF has been completed). However, if the investigator learns of any SAE, including a death, at any time after a subject has

been discharged from the study, and he/she considers the event reasonably possibly related to the study treatment or study participation, the investigator must promptly notify Lilly.

Pregnancy (maternal or paternal exposure to investigational product) does not meet the definition of an AE. However, to fulfill regulatory requirements any pregnancy should be reported following the SAE process to collect data on the outcome for both mother and fetus.

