## 9.6. Pharmacodynamics

### 9.6.1. Immunogenicity Assessments

For immunogenicity testing, venous blood samples of approximately 10 mL will be collected from each subject according to the Schedule of Activities (Section 2) to determine antibody production against LY3298176. Additional samples may be collected if there is a possibility that an AE is immunologically mediated. All samples for immunogenicity testing should have a time-matched sample for PK analysis where relevant. In the event of drug hypersensitivity reactions (immediate or non-immediate), additional samples will be collected as close to the onset of the event as possible, at the resolution of the event, and 30 ( $\pm$  3) days following the event. Instructions for the collection and handling of blood samples will be provided by the sponsor. The actual date and 24-hour clock time of each sampling will be recorded.

Immunogenicity will be assessed by a validated assay designed to detect ADA in the presence of LY3298176. Antibodies may be further evaluated for their ability to neutralize the activity of LY3298176. Positive LY3298176 ADA samples may also be tested for cross-reactivity with native GLP-1 and GIP, and, if positive, may then be tested for neutralizing antibodies against native GLP-1 and GIP.

All subjects will have an ADA sample measured at early discontinuation or at the follow-up visit. A risk-based approach will be used to monitor subjects who develop treatment-emergent ADA (TE ADA), defined as a titer 2-fold (1 dilution) greater than the minimum required dilution of the assay if no ADA were detected at baseline, or a 4-fold (2 dilutions) increase in titer, compared to baseline, if ADA were detected at baseline. The minimum required dilution of the ADA assay is 1:10.

Clinically significant TE ADA will be defined as any TE ADA at the last visit with:

- a high titer ( $\geq$ 1280) or an increasing titer from last measured value
- an association with a moderate-to-severe injection-site reaction
- cross-reactive and/or neutralizing binding of an ADA with endogenous GLP-1 or GIP.

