- AUC(0-∞) values where the percentage of the total area extrapolated is more than 20% will be flagged. Any AUC(0-∞) value excluded from summary statistics will be noted in the footnote of the summary table.
- Half-life ($t_{1/2}$) will be calculated, when appropriate, based on the apparent terminal log-linear portion of the concentration-time curve. The start of the terminal elimination phase for each subject will be defined by visual inspection and generally will be the first point at which there is no systematic deviation from the log-linear decline in plasma concentrations. Half-life will only be calculated when a reliable estimate for this parameter can be obtained comprising of at least 3 data points. If $t_{1/2}$ is estimated over a time window of less than 2 half-lives, the values will be flagged in the data listings. Any $t_{1/2}$ value excluded from summary statistics will be documented in the footnote of the summary table.
- A uniform weighting scheme will be used in the regression analysis of the terminal log-linear portion of the concentration-time curve.
- The parameters based on the predicted last quantifiable drug concentration (C_{last}) will be reported.

Individual PK Parameter Rules

- Only quantifiable concentrations will be used to calculate PK parameters with the exception of special handling of certain concentrations reported below the lower limit of quantitation (BQL). Plasma concentrations reported as BQL will be set to a value of zero when all of the following conditions are met:
 - The compound is non-endogenous.
 - The samples are from the initial dose period for a subject or from a subsequent dose period following a suitable wash-out period.
 - The time points occur before the first quantifiable concentration.
- All other BQL concentrations that do not meet the above criteria will be set to missing.
- Also, where two or more consecutive concentrations are BQL towards the end of a profile, the profile will be deemed to have terminated and therefore any further quantifiable concentrations will be set to missing for the calculation of the PK parameters unless it is considered to be a true characteristic of the profile of the drug.

Individual Concentration vs. Time Profiles

- Individual concentrations will be plotted utilizing actual sampling times.
- The terminal point selections will be indicated on a semi-logarithmic plot.

Average Concentration vs. Time Profiles

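### Mandatory study exit for pancreatitis cannot reduce exposure after a single Day 1 dose; it cuts scheduled PK, ADA and safety follow-up short

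*Protocol*

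**What the plan says.** Appendix 7, in the notes to the pancreatic enzyme algorithm, rules that "Subjects diagnosed with pancreatitis will be discontinued from the study". The wording is mandatory and refers to the study, not the drug. The same notes ask for study drug to be stopped only where that applies.

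The protocol's Overall Design (5.1) describes a "multicenter, parallel, single-dose, open-label, single-period study of tirzepatide", and Table GPGQ.3 gives the dosing as "Single injection into abdomen on Day 1". Exclusion criterion [32] already removes people who "have a history or presence of pancreatitis".

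Section 8.1 sends early discontinuations to the Schedule of Activities, where follow-up and early discontinuation share one column. Its timing note reads "At least 28 days postdose or within 7 to 14 days upon confirmation of early discontinuation". That visit includes a PK sample, and Section 9.6.1 adds: "All subjects will have an ADA sample measured at early discontinuation or at the follow-up visit". Section 9.2.1 says: "Investigators are not obligated to actively seek AEs or SAEs in subjects once they have discontinued from and/or completed the study".

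Some follow-up survives exit. Appendix 7 requires the pancreatitis event to be followed until it resolves or is explained. Section 9.6.1 continues ADA testing for clinically significant treatment-emergent antibodies.

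**The concern.** A stopping rule normally protects the subject from further drug. Here all the drug has been given before the rule can act, so what it changes is data collection. It reads like multiple-dose wording carried into a single-dose trial. For hyperglycemia during follow-up, Section 9.4.2.1 does the opposite and keeps the subject in the study to the end of planned follow-up.

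Two things are at stake:

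- **Primary endpoint.** An early exit can leave too few terminal concentrations for AUC(0-∞). Cmax normally survives unless exit comes before the peak.
- **Secondary endpoint.** Scheduled adverse event observation ends early in a subject who has just had a serious event and still has drug on board. The half-life is about 5 days (Section 3.2).

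No direction of bias is claimed.

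**Working it through.** **Plan's own figure.** The Schedule of Activities lists PK samples at predose, 8, 12, 24, 48, 72, 96, 168 and 336 h and at follow-up, which is 10. With 3 unscheduled samples, (10 + 3) × 3 mL = 39 mL, matching Appendix 5.

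**Doses the rule can avoid after Day 1:** 0.

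**Visit timing.** Assume discontinuation is confirmed on the day of diagnosis. The last visit is then at exit day + 7 to + 14, and the loss is 28 minus that day.

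| Exit | Last visit (days postdose) | Days lost against 28 | Scheduled PK samples replaced | Net PK samples lost |
|---|---|---|---|---|
| 72 h | 10–17 | 11–18 | 4 | 3 |
| 96 h | 11–18 | 10–17 | 3 | 2 |
| 168 h | 14–21 | 7–14 | 2 | 1 |
| 336 h | 21–28 | 0–7 | 1 | 0 |

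From about 21 days postdose nothing is shortened. The net column allows for the one sample taken at the discontinuation visit.

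**AUC(0-∞).** The model is my assumption: one compartment with first-order absorption. Section 3.2 gives a half-life of about 5 days, so k = ln 2 / 120 h, and tmax between 24 and 72 h. Solving ln(ka/k)/(ka − k) = tmax gives ka = 0.138, 0.0513 and 0.0274 per h for tmax 24, 48 and 72 h. Samples up to exit are kept and one is added 168 or 336 h later. AUC uses the linear rule to tmax and the log rule after it. The terminal slope comes from the last three points, with predicted Clast.

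The SAP (9.3.1) states: "Half-life will only be calculated when a reliable estimate for this parameter can be obtained comprising of at least 3 data points". It does not say whether the Cmax point may be one of the three. The table shows the percentage extrapolated for a discontinuation visit at +7 d / +14 d.

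| Exit | tmax 24 h | tmax 48 h | tmax 72 h |
|---|---|---|---|
| 48 h | 31 / 12 (only if Cmax counts) | not estimable | not estimable |
| 72 h | 26 / 10 | 30 / 11 (only if Cmax counts) | not estimable |
| 96 h | 23 / 9 | 25 / 10 | 32 / 12 (only if Cmax counts) |
| 168 h | 15 / 6 | 16 / 6 | 20 / 7 |

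In the cells marked not estimable, one point remains after the observed Cmax, so even counting Cmax gives two. In every other cell AUC(0-∞) is within about 4% of the true value. Extrapolation above 20% is flagged by the SAP, not automatically excluded.

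**Drug still to be cleared at the last visit.** For exit at 72 h, 26–32% of AUC is still to come at day 10 and 10–12% at day 17. At day 28 the figure is 2–3%.

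**Cost of one lost value in Group 4.** Take 6/6/6/n subjects, so N = 18 + n. Four groups and one covariate leave N − 5 degrees of freedom. The 90% CI multiplies and divides the ratio by exp(t(0.95, N − 5) × s × √(1/6 + 1/n)), where s = √ln(1 + CV²). The plan gives no CV; 30% is assumed, so s = 0.2936.

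- n = 3: exp(1.746 × 0.2936 × 0.7071) = 1.44
- n = 2: exp(1.753 × 0.2936 × 0.8165) = 1.52
- n = 1: exp(1.761 × 0.2936 × 1.0801) = 1.75

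Over n = 3, 2, 1 the factors are 1.28, 1.33, 1.46 at CV 20% and 1.61, 1.74, 2.08 at CV 40%. In a full design of 6 per group at CV 30%, losing one value moves the factor only from 1.34 to 1.36.

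**The case against.** The strongest reply is that exit has a purpose other than reducing exposure. It spares an acutely ill subject research visits and blood draws in a trial that offers no therapeutic benefit. That is a fair aim, but Section 8.1 already lets the investigator or the subject end participation for such reasons. The Appendix 7 sentence adds only compulsion.

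The remaining points concern size, and they stand:

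- The event is unlikely. At most 30 subjects get one dose, and criterion [32] excludes prior pancreatitis and amylase or lipase above 1.5 times the upper limit.
- AUC(0-∞) is lost outright only for very early exits. Any delay in confirming discontinuation adds scheduled samples.
- At most one of three planned ADA samples is lost.
- Section 9.2 keeps other serious, medically important or related events under follow-up, and related SAEs learned of later must be reported. What ends is active seeking of new events.
- Safety analysis is descriptive.
- Replacement is allowed, although the protocol says Child-Pugh C subjects are hard to recruit.

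These points keep the severity low. None of them gives mandatory exit a function after Day 1.

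**Conclusion.** The concern holds and is minor. After the single dose the rule can prevent no exposure, and it exchanges the remaining scheduled assessments for one visit. The loss is material for diagnosis up to about Day 8, slight at Day 15, and nil from about 21 days postdose. An early exit can cost a subject's AUC(0-∞), which matters most if Group 4 has 2 or 3 subjects; otherwise the PK damage is slight.

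The textual finding needs no assumptions. The sizes rest on the one-compartment model, same-day confirmation of discontinuation and an assumed CV of 20% to 40%.

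**What to change.** Replace the Appendix 7 sentence with: *Because dosing is complete on Day 1, a post-dose diagnosis of pancreatitis does not by itself end study participation. Scheduled PK, ADA and safety assessments through at least 28 days postdose continue where the subject agrees and the investigator considers them safe.*

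Leave clinical management, SAE reporting and the withdrawal options in Section 8.1 as they are.

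The cost is one sentence in a protocol amendment. A subject with pancreatitis may be asked for a few more visits and 3 mL PK samples, which the subject can refuse or the investigator can stop.
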